5.2 Recruitment Methods

Recruitment and Informed Consent

Aim 1: Participation in the randomized controlled trial portion of the study will involve obtaining a signed informed consent document from subjects. This process is described under Aim 2 below.

We will seek a waiver of informed consent to conduct the hand hygiene observations for Aim 1 on each unit and with each physician team that participates in the trial. To help minimize a Hawthorne effect we will make these observations covertly by standing in the hallway and not following any one individual or team. If asked about our presence on the unit we will respond that we are there to study hospital workflow. The data collected will be de-identified, only indicating the role of the person observed (attending, senior, intern, or nurse). Hand hygiene is something that the hospital is already monitoring periodically and collecting hand hygiene data for this study will not put the observed healthcare providers at any increased risk.

Aim 2: The providers will be recruited through multiple methods to increase the participation rate.

- Nurses: We estimate there will be approximately 20-30 nurses on each unit. We will recruit from 2 units at the Ann Arbor VAMC (approximately 20 intervention; 20 control) and 4 units at the MEDVAMC (approximately 40 intervention; 50 control), for a total of approximately 130 nurse participants. Nurses will be provided information about the study during unit meetings and through study flyers posted in the break room (**Appendix H & I**).
 - Nurses on the control units will only be asked to complete the 3 study surveys over a 7-month period. This can be done with a waiver of documented consent. Nurses on the control units will be given a study information letter with a paper survey and return envelope or emailed the study information letter with a link to complete the survey electronically (**Appendix E**). If they complete the survey, they are implying consent. A reminder email will be sent at 1-week and 2-weeks to non-respondents to encourage participation (**Appendix F**).
 - Nurses on intervention units will be sent an introductory email (**Appendix J**) with information about the study and asking to set up a time and place to discuss the study in more detail. If we are unable to reach the nurses through email, study staff will approach the nurses during their work shift and ask to set up a time to meet to discuss the study in private. Recruitment will occur in a private room or office using the attached recruitment script (**Appendix K**).
- Physicians: We estimate enrolling approximately 35 attending physicians, 24 senior residents, and 48 intern physicians into each arm of the study, which will result in a total of 214 physicians in total. All physicians from physician teams will be asked to participate in the randomized controlled trial and provide a signed informed consent. Each month one team at the Ann Arbor VAMC and 2 teams at MEDVAMC will be randomized to intervention and an equal number at each site will be randomized to control. A flyer describing the study (**Appendix S**) will be emailed (**Appendix T**) to teaching attendings to introduce the study. Before the beginning of the month, the initial attending physician on each selected team will be sent an email describing the study and giving them the option to opt out of their team being approached to participate (**Appendix L**). A time and place will be scheduled to discuss the study in more detail and obtain informed consent from the attending (**Appendix M**). Unless the attending indicates they do not want their team participating, the rest of the team will be sent an email describing the study (**Appendix L**). Then study staff will approach the senior resident and interns in the team rooms and ask to speak with them about the study (**Appendix M**). If there are others in the team room, the study staff will ask the residents to follow them to a private room to discuss the study in greater detail. If they are willing to participate, they will be asked to sign an informed consent document. The primary participants are the attending physicians on each team. If the initial attending declines allowing their team to participate, another team will be randomly selected and approached for participation. If any physicians choose to not participate, they will not be asked to participate in the intervention activities (if randomized to the intervention) or to complete the study surveys (both study

arms). However, hand hygiene data will still be collected using a waiver of informed consent. When a new attending starts on a team that has already been randomized, they will be recruited in a similar manner as the initial attending (email, followed by in person recruitment). If the 2nd attending on the team declines participation, the team is still considered enrolled, however the new attending will not be asked to participate in the intervention (if on an intervention team) or complete the study surveys.

Aim 3: Interviews and Guided Discussions

- Interviews: Select participants in the intervention arm will be asked to participate in the qualitative evaluation interviews to provide feedback about the intervention. We estimate enrolling 4-6 nurses and 8 physicians from each site. The providers will be recruited via email (**Appendix N**) or in-person communication with study staff. If they agree, a day, time, and location for the interview will be arranged. At the Ann Arbor VAMC, these interviews can be conducted in person, or by phone if needed. Members of the team from Ann Arbor plan to travel to MEDVAMC to conduct these interviews in person as well, since more information can be obtained through direct observation and face to face interactions. However, if travel restrictions are in place or if someone is unable to attend an in-person meeting, the interview can be scheduled to occur either over the phone or using a VA approved conferencing program like Microsoft Teams or Zoom for Government. The Ann Arbor qualitative team will provide a study information letter and review the purpose of the interview before obtaining verbal informed consent. As we will be audio recording – will ask verbal permission to audio record at the start of the interview using the attached audio recording permission script (**Appendix O**). We will ask for a waiver of informed consent for this aim of the study as it poses minimal risk and a signed consent would be the only link between the subject and their interview, which would increase their risk of loss of confidentiality.
- Guided Discussions: The signed informed consent that is obtained from all nurses and physicians in the intervention will include permission to record the guided discussion sessions. In addition, the mindfulness champion will ask all attendees at each guided discussion session if they are willing to have the session recorded and that they can ask to have the recorder turned off at any time for any reason (**Appendix P**).

All subjects will be VA employees or trainees. As participation in this program will require extra time outside of their normal work duty to complete the three mindfulness educational modules, we will offer \$25 remuneration per completed module (maximum of \$75 for the project). Each participant will be given a unique code to access these training modules. Consultant [name] will email the project manager every 1-2 weeks with a list of which modules were completed and the associated unique codes. The staff in Ann Arbor will then check the cross-link file to identify to which subjects those codes correspond. The gift cards will then be mailed to the participants for each completed module or distributed in person where feasible. This is to help promote completion of this key part of the intervention. Participants will be told they will not be

eligible for remuneration if they complete the modules during their normal working hours. However, this will be done on an honor system as project staff will have no way to confirm when the modules were completed or what is the participant's normal tour of duty. There will be no remuneration for any other aspect of the project.

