5.0 Study Procedures

5.1 Study Design

Research Design: A multi-center, repeat-measures randomized controlled mixed-methods trial.

Study Population: The proposed study will focus on Internal Medicine physicians who are part of inpatient care teams and nurses providing care on medical and medical/surgical units at LTC Charles S. Kettles VAMC in Ann Arbor, MI and MEDVAMC in Houston, TX. Medical students, surgical physicians, and physicians on sub-specialty teams will not be included. At both participating facilities the inpatient care teams are predominately composed of 1 attending, 1 senior resident, 2 interns, and up to 3 medical or physician assistant students. Interns and senior residents are usually assigned to a team for 4-week blocks (occasionally 2 weeks), while attendings rotate approximately every 2 weeks. The Ann Arbor VAMC has 3 medical or medical/surgical inpatient units, while MEDVAMC has 5 units. At both facilities each nursing unit employs between 20-30 nurses. We will aim to recruit approximately 30 attendings, 72 residents and 40 nurses at Ann Arbor VAMC. As MEDVAMC is larger, with a greater number of inpatient care teams and nursing units than the Ann Arbor VAMC, we will aim to recruit approximately 40 attendings, 72 residents and 90 nurses. Our target study sample size is a total of 344 physicians and nurses (167 intervention/177 control). For Aim 3, we plan to interview approximately 8 physician team members and 4-6 nurses from the intervention arm at each site.

General Study Overview and Outcome Measures:

A summary of the proposed study activities at each participating site is presented in **Table 2** below.

Table 2: Overview of Study Activities at Each Study Site

| Study Detail | Physicians | Nurses |
|----------------------------------|--|--|
| Target | Attendings, senior residents and interns on inpatient medicine teams | Nurses on medical or medical/surgical units |
| Teams/Units Participating | 2 teams each month for 12 months randomized to intervention or control arm at each site | 2 units (1 intervention; 1 control) at Ann Arbor VAMC & 4 units (2 intervention; 2 control) at MEDVAMC randomized once & followed for 12-months |
| Estimated number of participants | 107 intervention and 107 control | 20 intervention and 20 control at Ann Arbor VAMC; 40 intervention and 50 control at MEDVAMC |
| Habituation Period | 1 month | 1 month |

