Power - Based on a range of 10%-15% significant percent change in hand hygiene adherence from our pilot data,⁷² we are anticipating an expected increase in hand hygiene adherence due to the intervention from approximately 80% at baseline to 88%-92% at follow-up. We will have 79.8% power to detect this 10% increase based on a fixed total sample size of 334 with a two-sided alpha of 0.05, assuming an average of 60 observed hand hygiene opportunities per provider per measurement time point (i.e., intervention and follow-up), and taking into account clustering of data within site/team/unit (assumed Intraclass Correlation Coefficient=0.4).⁸² For assessing differences in the select PSHW questions we will have 70.1% power to detect an effect size of 0.15.⁸³ For assessing differences in FFMQ and WBI scores, we will have >95% power to detect effect sizes ranging from 0.3 to 0.75 as found in prior studies.^{65,84,85}

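### The protocol gives two totals (344 and 334), and on its best-supported team count the resident target takes up every post, with no stated allowance for refusal or survey non-response

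*Protocol*

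**What the plan says.** Protocol section 5.1 (Study Population) states: "Our target study sample size is a total of 344 physicians and nurses (167 intervention/177 control". Section 5.2 supplies the physician part, "We estimate enrolling approximately 35 attending physicians, 24 senior residents, and 48 intern physicians into each arm of the study", and the nurse part, "for a total of approximately 130 nurse participants". The power paragraph in section 5.6 instead uses a "fixed total sample size of 334". The SAP gives no sample size or power.

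Teams and posts are described in several places:

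- Section 5.1 (Table 2, Randomization, Intervention Assessment): two teams per site per month, one per arm, for 12 months, so up to 24 teams per site.
- Section 5.1 (Data Collection and Management): up to 48 teams at each site.
- Section 5.2: each month, one Ann Arbor team and two MEDVAMC teams go to intervention, with equal numbers to control.
- Team make-up: one senior and two interns in section 5.1, but two to three interns in section 5.4.

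On refusal, section 5.2 says: "If any physicians choose to not participate, they will not be asked to participate in the intervention activities". Refusers are also not surveyed. A replacement team is sought only when the initial attending declines. Hand hygiene is still observed for refusers under a waiver of consent.

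For nurses, section 5.1 says "each nursing unit employs between 20-30 nurses", and Table 2 plans "40 intervention and 50 control at MEDVAMC".

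**The concern.** An enrolment target should be the number of eligible people multiplied by an expected consent rate. If the target equals the number of posts, no consent rate has been applied. Here participation is voluntary, refusal is provided for, and the risk section expects many residents to have moved to other hospitals by follow-up. No consent or survey-response rate is stated.

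Two populations also appear to share one number: providers observed without consent (Aim 1 adherence and duration), and providers who consent and return surveys (PSHW, FFMQ, WBI). At stake is whether the survey power stated in section 5.6 describes the people who will actually be analysed. Separately, a total described as fixed should agree with the target elsewhere in the same protocol.

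**Working it through.** **1. Reproduce the target.**

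- Physicians: 2 × (35 + 24 + 48) = 214. Nurses: (20 + 20) + (40 + 50) = 130. Total: 214 + 130 = 344.
- By arm: 107 + 60 = 167 and 107 + 70 = 177.
- By site: 30 + 72 + 40 = 142 and 40 + 72 + 90 = 202, which sum to 344.

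So 344 reproduces by arm, role and site, and 334 does not. The gap is 10 people (10/344 = 2.9%). A total of 334 would equal 214 + 120, as if MEDVAMC control nurses numbered 40 and not 50, but that origin is an inference.

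**2. Resident target as a share of posts, per arm.** Posts = team-months × (1 senior + interns per team). Target = 24 + 48 = 72.

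| Team-months per arm | Interns per team | Posts | Target / posts |
|---|---|---|---|
| 24 (5.1) | 2 (5.1) | 72 | 100% |
| 24 (5.1) | 3 (5.4, upper) | 96 | 75% (seniors still 24 of 24) |
| 36 (5.2) | 2 | 108 | 67% |
| 36 (5.2) | 3 | 144 | 50% |

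At 36 team-months and two interns, Ann Arbor still has 24 teams over both arms, so 72 posts for its target of 72. MEDVAMC has 48 teams, so 144 posts for its target of 72 (50%). The site targets in section 5.1 give 72 residents at both hospitals. That equality fits two teams per site per month, so the 24-team reading is the better supported.

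**3. Other roles.**

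- Attendings rotate about every two weeks: 24 × 2 = 48 slots per arm against a target of 35 (73%), with repeat service allowed.
- Nurses: six units of 20–30 employ 120–180, against a target of 130. The 50 MEDVAMC control nurses come from two units employing 40–60, which is 50/60 = 83% to 50/40 = 125%.

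**4. Effect on survey power.** The sizes below are illustrative: 344 × 0.80 = 275 and 344 × 0.64 = 220, where 0.80 and 0.64 are assumed fractions of the target analysed. Power is from the noncentral t distribution, two-sided alpha 0.05, equal arms, no clustering. The effect is d = 0.3, the smallest for which section 5.6 claims more than 95% power for FFMQ and WBI.

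| Total analysed | Two-arm comparison | Within-arm paired test |
|---|---|---|
| 344 | 79% | 97% |
| 334 | 78% | 97% |
| 275 | 70% | 94% |
| 220 | 60% | 88% |

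The noncentrality is d/√(1/n₁ + 1/n₂) for two arms and d√n for n pairs. Paired power reaches 95% at 147 pairs (95.1%) and is just under it at 146. That is 147/167 = 88% of the intervention-arm target.

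If only residents and interns refuse, on 72 posts per arm, the total is 344 − 144 × (1 − consent). At assumed consent of 90%, 80%, 70% and 60% this gives 330, 315, 301 and 286.

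**The case against.** **The full-roster result depends on the reading.** This is correct. Section 5.2 itself gives a team count under which the target is two-thirds of posts, and a third intern also leaves room. A reader might infer that every resident must consent on any reading, and the documents do not support that. The figure of up to 48 teams per site in section 5.1, and the observation totals there that use 24 attending teams per arm per site, may count two-week attending blocks, but the text does not say so. Occasional two-week resident blocks would also supply more people than posts.

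**The target does not equal posts for every role.** Also correct. Attendings are below their slots. The overall nurse target exceeds staffing only near the lower unit size, and both nurse figures are approximate.

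**A large shortfall is not shown.** A reader might infer that Aim 2 will be analysed on far fewer than 344 people. Without consent or response rates this is a possibility and not a finding. Applying assumed consent to 344 could also discount twice for attendings and nurses, whose targets may already allow for refusal. The stated 70.1% for PSHW is close to the 69.8% that a paired test at 0.15 gives with 275 people, so some loss may have been assumed, but the protocol does not say so.

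**The planned models do better than a simple two-arm test.** Partly so. The protocol's ANCOVA adjusts for baseline. With an assumed baseline correlation of 0.7, two-arm power at d = 0.3 is 97% at 344 and 93% at 275; with 0.5 it is 89% and 82%. The SAP's mixed models keep partial responders, and reminders are planned. None of this restores people who never consent, and no correlation is stated.

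**The primary outcomes are untouched.** Correct as regards numbers observed: Aim 1 adherence and duration include refusers under the waiver.

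**Conclusion.** The point holds in limited form. The protocol contradicts itself on the total (344 against 334), on teams per month, and on interns per team. On the best-supported team count with two interns, the resident and intern target is 100% of posts, although individual refusal is foreseen without replacement. No allowance for consent or response is stated on any reading.

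The consequence is confined to the survey outcomes. The 344/334 difference is worth about one point of power (79% against 78% in the two-arm calculation) and is a consistency correction. The larger matter is that the survey power rests on a number with no stated route from eligible staff to completed surveys. Even on the within-arm paired reading, the claim of more than 95% at d = 0.3 fails once fewer than about 147 pairs per arm remain, a loss of just over 12% of the intervention target. These power figures ignore clustering and use assumed sample sizes, so they show sensitivity and do not forecast the shortfall.

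**What to change.** - Reconcile the number of teams per site, arm and month, and the interns per team, across sections 5.1, 5.2 and 5.4. Say whether the 48 per site counts attending blocks.
- Use one total in sections 5.1 and 5.6, and check the MEDVAMC control-nurse target against the staffing of the two units.
- State two sizes. Providers observed under the waiver are everyone on the selected teams and units; this should not be labelled 344. The expected survey sample is eligible posts × assumed consent × assumed response, by role and time point.
- Restate the PSHW, FFMQ and WBI power in section 5.6 at the expected survey sample, for the planned between-arm analysis, giving any baseline correlation and clustering assumed.

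The change is to wording and a recalculation. Its cost is that the stated Aim 2 size and power become less favourable. No extra enrolment is needed.

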5.3 Informed Consent Procedures

Subjects will be recruited for the project as described in section 5.2. We will seek a waiver of informed consent to conduct the hand hygiene observations for Aim 1.

All physician participants (i.e., those that are assigned to either the intervention or control arm of the study) will be asked to provide written informed consent with a HIPAA authorization. The informed consent document will describe the randomized controlled trial including both arms of the study (intervention activities and control). It will also include information about the survey data that they would be asked to provide at baseline, 1-month, and 6-month post-intervention time-points. This method of consent will allow the research assistants who will be obtaining the informed consent and also conducting the hand hygiene observations to be blinded to the intervention status of each participant.

For nurse participants, we will seek a waiver of documented informed consent for the nurses on the units randomized as control. These nurses will only be asked to complete surveys about mindfulness (**Appendix B**) at baseline, 1, month, 6 months post-intervention. Completion of surveys falls under exemption category 2. Completing the survey will imply their consent for their responses to be included in the study. The nurses on the units randomized to the intervention will be asked to provide written informed consent to participate in the intervention which will outline all aspects of the intervention as well as the surveys. This change in consent strategy between the nurses and physician is because the research assistants will know which units are assigned to intervention and control. It is not feasible to blind the research assistants to the intervention status of the nursing units, but we will be able to blind them to the status of the physicians. As such, we are requesting the waiver of documented consent for the control nurses only to reduce burden in the hopes of increasing participation of this group.

For the physicians (both intervention and control) and the nurses on the intervention units, consent will be obtained in a private room or office. Trained research staff will explain the study and answer any questions. If the eligible subjects choose to participate, they will then be asked to provide a signed informed consent which will cover the appropriate aspects of the study.

For the interviews of a sample of intervention participants for Aim 3, the qualitative team will provide a study information letter and review the purpose of the interview before obtaining verbal informed consent. We will ask for a waiver of documented informed consent for this portion of the study as it poses minimal risk and a signed consent would be the only link between the subject and their interview, which would increase their risk of loss of confidentiality. All study research staff will be trained in appropriate human subjects protection and the informed consent process. To minimize

the risk of coercion, all potential subjects will be offered the opportunity to decline study participation with no penalty to VA employment, and will be informed that they may decide not to continue participation at any time. As our subjects are VA staff, there will not be any protected health information collected as part of this project.

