Randomization – At each study site the participating physician teams and nursing units will be randomly assigned into one of two study arms (intervention/control). For physician teams, this will occur on a rolling basis for 12 months with 2 physician teams randomly selected at each site each month for participation (1 intervention, 1 control). Once randomized, an email will be sent to the initial attending of the team introducing the study and asking them to reply to the email if they would prefer to opt out and not have their team participate in the randomized controlled trial. If the attending physician from a team refuses to allow their team to participate, the next team identified from the randomized list will be approached to participate. If a new attending joins the team mid-month, they will be approached to participate in the study, but will be automatically assigned to the same randomization group as the rest of their team.

Similarly, a total of 2 medical/surgical units from VAAHS (1 intervention, 1 control) and 4 medical/surgical units from MEDVAMC (2 intervention, 2 control) will be randomly selected to participate in the nurse portion of the project. The nurse manager for each

selected unit will then be approached to obtain approval for the unit to participate. If a nurse manager declines, the next unit on the list will be selected.

For both physicians and nurses, an independent statistician will allocate the teams and units in a concealed fashion, using a computer-generated randomization schema. The physicians and nurses from the intervention groups will receive both independent and group-facilitated mindfulness education, will be encouraged to use a mindfulness mobile app as a practice reminder and additional resource, and instructed to integrate moments of mindfulness with repeated episodes of hand hygiene during the course of caring for patients. The control groups will receive no such education or intervention and will continue as usual.

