transport to protect confidentiality. Once in a study office, the hand hygiene observation data will be entered into a study database on a secure VA server, with access only to study team members. The paper observation forms will be stored in a locked filing cabinet.

Aim 2: All potential participants will be clearly informed that their participation is completely voluntary. Thus, an alternative course of action for each of them would be to not participate. Subjects will be asked to complete surveys with questions on mindfulness and well-being at multiple time points throughout the study. These surveys will be labeled with a unique study ID so study staff can link the survey to the subject. The crosswalk file that would identify the participants will be stored on a secure VA server with access to only study staff. The baseline survey will primarily be distributed in paper form when participants are recruited, after they have provided informed consent. The data from these surveys will be entered into a study database on a secure VA server and then stored in a locked filing cabinet. We will also distribute surveys electronically to those we are unable to approach in person. For example, nurses on the control units will be emailed an invitation to participate in the study survey instead of in person (**Appendix E**). A reminder email will also be sent to non-respondents on the nurse control units to encourage participation (**Appendix F**). We will also email the 1-month and 6-month post-intervention (7 months from baseline) surveys to nurses on the intervention units, as well as physicians during follow-up since many resident physicians will rotate to other hospitals (**Appendix G**). Similar to the nurse control's, reminder emails will be sent to non-respondents at 1-week and 2-weeks after the initial mailing to encourage survey completion (**Appendix F**). We will use an online survey program like Qualtrics which can be accessed outside of the VA firewall, since physicians may be completing the survey on a non-VA computer. The electronic surveys will not contain any individual identifiers. They will be labeled only with the unique study ID number and will ask questions about mindfulness, well-being and hand hygiene perceptions.

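### Nurses consent and give their baseline survey after their unit's arm is known, by a different consent route in each arm, which risks selection bias and an allocation-affected baseline in the nurse survey comparisons

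*Protocol*

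**What the plan says.** Protocol 5.1 (Randomization) allocates nursing units, not nurses. At the larger site, "4 medical/surgical units from MEDVAMC (2 intervention, 2 control) will be randomly selected to participate in the nurse portion of the project"; the other site contributes one unit per arm. The nurse manager, and then the nurses, are approached only after that step.

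Protocol 5.3 sets the consent by arm. On intervention units, "The nurses on the units randomized to the intervention will be asked to provide written informed consent to participate in the intervention", and that form describes the surveys as well as the programme. For the others, "we will seek a waiver of documented informed consent for the nurses on the units randomized as control". Protocol 5.2 says of control nurses: "If they complete the survey, they are implying consent". Intervention nurses are recruited in a private meeting with a script (5.2).

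Protocol 5.3 gives two reasons for the difference: "the research assistants will know which units are assigned to intervention and control", and the waiver for control nurses is meant "to reduce burden in the hopes of increasing participation of this group". Physicians in both arms sign one form that describes both arms, and their recruiters are blinded.

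The baseline survey follows consent (5.1, Pre-Intervention Assessment, and the Aim 2 text under Risks). On survey mode, the Risks text says "nurses on the control units will be emailed an invitation to participate in the study survey instead of in person", while 5.2 also allows control nurses a paper survey.

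**The concern.** When clusters are randomised first and individuals recruited afterwards, the arms are comparable only if joining does not depend on the arm. Here it may. An intervention nurse is offered the surveys as part of an agreement to a mindfulness programme, and no survey-only route is described. A control nurse is asked only for three surveys. The two groups of joiners may therefore differ in motivation, in interest in mindfulness, or in spare time.

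Intervention nurses also answer the baseline FFMQ, WBI and PSHW items after reading about the programme they are to receive. The score used for adjustment can then itself be affected by allocation.

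At stake are the nurse contributions to the Aim 2 outcomes (FFMQ, WBI) and to the PSHW perceptions, a secondary Aim 1 outcome. Hand hygiene is observed under a waiver whoever joins, so the Aim 1 primary outcomes do not depend on this.

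**Working it through.** **Order of events.** Protocol 5.1 describes the pre-intervention assessment before the randomisation paragraph, which could suggest that baseline comes first. For nurses it cannot. The survey follows consent, and the form of consent depends on the unit's arm (5.2, 5.3). The order is allocation, then arm-specific consent, then baseline.

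**What the analysis adjusts for.** The Protocol (5.6) uses ANCOVA on the pre-test score. The SAP uses a mixed model with clinician random effects, adjusted for role and fidelity. Either handles much of a stable level difference between joiners and non-joiners. Neither removes selection on motivation or responsiveness, or a shift in baseline answers caused by knowing the arm. Neither document plans participation rates by arm, a comparison of joiners with non-joiners, or a sensitivity analysis on this point.

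**Counts (Protocol 5.1 and Table 2).**
- Intervention: 107 physicians + 20 + 40 nurses = 167
- Control: 107 physicians + 20 + 50 nurses = 177
- Total: 167 + 177 = 344, which reproduces the stated target
- Nurses: 60 + 70 = 130, and 130/344 = 38%

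**Illustration of size.** Assumptions not in the documents: 30 nurses on every unit (the top of the stated range of 20-30), a joiner/non-joiner difference d of 0.2-0.5 SD, no baseline adjustment, and independent responses.
- Participation p: intervention 60/90 = 0.667; control 70/90 = 0.778.
- Shift of joiners from their whole unit = (1 - p) x d. Intervention: 0.333 x 0.2 = 0.067 to 0.333 x 0.5 = 0.167. Control: 0.222 x 0.2 = 0.044 to 0.222 x 0.5 = 0.111.
- Pooled bias weights each arm's shift by its nurse share: 60/167 = 0.359 and 70/177 = 0.395.
- Standard error: nurses, sqrt(1/60 + 1/70) = 0.176; pooled, sqrt(1/167 + 1/177) = 0.108.
- Two-sided type I error = 1 - Φ(1.96 - bias/SE) + Φ(-1.96 - bias/SE).

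| Selection | Nurse bias (SD) | Type I error, nurses | Pooled bias (SD) | Type I error, pooled |
|---|---|---|---|---|
| Intervention arm only | 0.07-0.17 | 6.7%-15.7% | 0.02-0.06 | 5.6%-8.6% |
| Both arms, same direction | 0.02-0.06 | 5.2%-6.1% | 0.006-0.016 | 5.0%-5.2% |
| Opposite directions | 0.11-0.28 | 9.7%-35.2% | 0.04-0.10 | 6.7%-16.1% |

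With 25 nurses per unit, intervention participation is 60/75 = 0.80. Selection in that arm only then gives 0.04-0.10 SD among nurses and 0.014-0.036 SD pooled. With 20 per unit, the intervention target equals the whole staff and this source of bias vanishes in that arm.

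**Role-adjusted pooling.** The SAP adjusts for role. The nurse weight is then 60 x 70/130 = 32.3 against 107 x 107/214 = 53.5 for physicians, so 32.3/85.8 = 0.38. Applied to 0.067-0.167, this gives 0.025-0.063 SD, close to the simple pooled figures.

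**The case against.** The best defence is that the effect on the trial-wide estimate may be small. The analysis combines nurses with physicians, whose consent is symmetrical and whose recruiters are blinded. Baseline adjustment deals with much of a level difference, which is the part quantified above. Both points stand. They limit the size but do not reach selection on motivation or an allocation-affected baseline.

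A reader might also infer stronger things that the documents do not support:

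- **That the targets prove unequal uptake.** Table 2 gives "40 intervention and 50 control at MEDVAMC" from equal numbers of units. Units employ 20-30 nurses and the targets are approximate, so unit size could explain the gap. The other site plans 20 v 20. The power section's total of 334 equals 2 x 167, which may reflect equal arms (an inference).
- **That selection alone uses up a third of the planned effect.** With 25 nurses per unit and a 0.5 SD difference, 80% uptake gives 0.2 x 0.5 = 0.10 SD, against the smallest planned effect of 0.3. That compares an unadjusted shift among nurses at one site with an effect size quoted for the whole trial. Pooled, it is about 0.10 x 32.3/85.8 = 0.04 SD if it applies to all nurses. If it applies to the larger site only, the weight is 40 x 50/90 = 22.2 and the figure is 0.10 x 22.2/85.8 = 0.03 SD.
- **That nurses drawn to mindfulness join one arm only.** Control nurses are also invited to surveys about mindfulness, so selection can occur in both arms.
- **That survey mode differs cleanly by arm.** The Aim 2 text under Risks has email for control nurses, but 5.2 allows paper or email, and 5.1 elsewhere says in person where feasible. Emailed follow-up surveys are planned for intervention nurses too. The mode statements are inconsistent; they do not amount to a settled difference between arms.

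**Conclusion.** The concern holds as a design risk. It rests on three things that the Protocol states outright: units are allocated before nurses are approached, consent is bundled with the programme in one arm and implied in the other, and baseline follows consent. That the nurse arms will in fact differ at baseline is not established, and neither the size nor the direction of a bias can be derived from the documents.

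The ranges above depend on the assumed unit size, the assumed joiner/non-joiner difference and the pattern of selection. Under one-arm selection, the pooled figure of 0.02-0.06 SD is 8%-20% of the smallest Aim 2 effect in the power statement (0.024/0.3 to 0.060/0.3), before any baseline adjustment. A nurse-only reading would be more exposed. The change is worth making because it is cheap and removes a risk that the model can only partly repair.

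**What to change.** - After the covert pre-intervention observation month ends, and before unit arms are disclosed to nurses, give the baseline survey to all nurses on all selected units. Use one information letter, one implied-consent route and one mode. It should not fall within the observation month, because its hand hygiene questions could prime the behaviour being observed.
- Then seek written consent from intervention-unit nurses for the intervention activities only.
- Send follow-up surveys to every baseline responder by the same mode in both arms. Analyse each nurse with a baseline survey in the unit's arm, whether or not the programme is taken up.
- Reconcile the survey-mode statements in 5.1 (Pre-Intervention Assessment, Data Collection and Management, and the Aim 2 text under Risks) with 5.2.
- If nurse enrolment is already over, report the numbers eligible, approached and joined by unit, and add nurse-only and physician-only analyses of the survey outcomes.

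The cost is an amendment extending the waiver of documented consent from control nurses to all nurse surveys, and a change in the order of steps. The estimate will be diluted slightly by intervention-unit nurses who answer the surveys but do not take up the programme.
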